## 1.2 Rationale for Evaluating CX-8998 in Idiopathic Generalized Epilepsy with Absence Seizures

### 1.2.1 Cav3 and its Role in Neurological Disorders with Excessive or Abnormal Rhythmicity

Calcium is a ubiquitous intracellular second messenger critical for cellular functions. The elevation of free intracellular  $\text{Ca}^{2+}$  levels triggers various responses, including the activation of  $\text{Ca}^{2+}$  dependent enzymes, the secretion of neurotransmitters, and muscle contraction. Multiple calcium ion channels regulate calcium influx in response to membrane depolarization, voltage changes, or substrate, which include the pore-forming alpha1 subunit Cav3 channel (Catterall, 2005; Adams & Snutch, 2007).

The T-type calcium channel, Cav3, its 3 isoforms (3.1, 3.2 and 3.3), and their genes *CACNA1G*, *CACNA1H*, and *CACNA1I* were discovered and cloned in the early 1990s, where their function as low-threshold, voltage-gated calcium channel was elucidated (Cribbs et al., 1998). T-type ("T" is for transient) calcium channels are low voltage-activated channels predominantly found in neurons. As stated previously, a unique and discriminating property of T-type channels (Cav3) is their ability to activate upon small depolarization of the membrane, contributing to the setting of the resting membrane potential and allowing a surge of calcium entry into excitable cells at the beginning of an action potential. In pathologic states, Cav3 is either upregulated or found to have increased activity, becoming a selective target for specific neurologic diseases (Bourinet et al., 2005; Park et al., 2010; Tai et al., 2011).

Isoforms of Cav3 are expressed throughout the central nervous system (CNS) and the peripheral nervous system, including the thalamocortical pathway (Ertel et al., 2000). Deep cerebellar nuclei, substantia nigra, globus pallidus externa, globus pallidus interna, subthalamic nucleus, have been noted to have oscillations in healthy hosts and excessive rhythmicity in animals and humans with pathologic conditions of the nervous system. It has been discovered that Cav3 is a mediator of subthreshold oscillations and excessive rhythmicity in pathophysiologic states found in tremor, neuropathic pain, epilepsy and Parkinson's disease (Llinás et al., 1999; Llinás, 2003; Handforth et al., 2005; Park et al., 2013).

### 1.2.2 Role of Cav3 in Epilepsy

It is well established that T-type calcium channels are a pharmacological target for absence seizures. Neuronal burst-firing, a key pathophysiologic contributor to epileptic seizures, is generated by low threshold calcium potentials initiated by Cav3 channel opening (Cain & Snutch, 2013). In particular, rodent models of absence epilepsy show enhanced Cav3 currents in thalamocortical relay neurons and enhanced burst-firing during seizures that correlate with spikes in spike-and-wave discharges. A number of single nucleotide mutations in Cav3.2 have been reported in patients with childhood absence epilepsy (Chen et al., 2004), some of which result in gains of function in channel gating and in elevated channel expression (Khosravani et al., 2004;

---

[figure not shown]
 Cav3.1 is the most common isoform in the thalamocortical pathway

[Vikto et al., 2005](#); [Peloquin et al., 2006](#); [Vikto et al., 2007](#)). In addition, overexpression of  $\text{Ca}_v3.1$  results in an absence-like seizure phenotype in mice ([Ernst, et al., 2009](#)) and mice lacking  $\text{Ca}_v3.1$  show reduced thalamocortical burst firing and resistance to pharmacologically induced absence seizures ([Kim et al., 2001](#)). A number of antiepileptic drugs have been reported to have nonselective  $\text{Ca}_v3$  blocking activity, including ethosuximide, valproate, zonisamide, and phenytoin ([Powell et al., 2014](#)). These drugs are thought to act in part through suppression of  $\text{Ca}_v3$  activity although all have substantial effects on other types of channels, including sodium, potassium, and potassium-activated calcium currents. Current treatments for absence seizures include ethosuximide, valproate, and the sodium channel blocker lamotrigine. In CAE, ethosuximide and valproate result in the best efficacy, with approximately 50% of patients achieving freedom from seizures, however, nearly a quarter of patients receiving these drugs experience intolerable side effects ([Glauser et al., 2010](#)). Thus, selective targeting  $\text{Ca}_v3$  channels may offer a more efficacious and better-tolerated treatment option.

### 1.3 Nonclinical Pharmacology

**Figure 1 Chemical Structure of CX-8998**

#### 1.3.1 Primary Pharmacology Studies

A large black rectangular redaction box covers the majority of the page content, starting below the header and ending above the footer. The redaction is irregular at the top right corner, suggesting it was cut out from a scanned document.

### 1.3.2 Safety Pharmacology and Toxicology Studies

11. **What is the primary purpose of the following statement?**

**SELECT \* FROM table\_name;**

A large black rectangular redaction box covers the majority of the page content, starting below the header and ending above the footer. The redaction is irregular, with some white space visible at the top and bottom edges.

## 1.4 CX-8998 Clinical Experience

**Table 1** Completed Clinical Studies

randomized; TETRAS = The Essential Tremor Rating Assessment Scale

### 1.4.1 Clinical Pharmacokinetics

## 1.4.2 Clinical Pharmacodynamics

### 1.4.3 Clinical Safety

[REDACTED]

[REDACTED]

[REDACTED]

[REDACTED]

## 1.5 Rationale for Selected Dose

[REDACTED]

100% of the time, the system is able to correctly identify the target class for the test samples.

100% of the time, the *hedgehog* is a hedgehog, and the *cat* is a cat. The *hedgehog* is not a *cat*, and the *cat* is not a *hedgehog*.

100% of the time, the *hedgehog* is a hedgehog, and the *cat* is a cat. The *hedgehog* is not a *cat*, and the *cat* is not a *hedgehog*.

11. **What is the primary purpose of the *Journal of Clinical Endocrinology and Metabolism*?**

## **2 STUDY OBJECTIVES**

### **2.1 Primary Objective**

- To assess the safety and tolerability of CX-8998 in adolescents and adults with IGE with absence seizures

### **2.2 Secondary Objectives**

- To evaluate the PK of CX-8998 and its metabolites (including, but not limited to, M01 and M02) in the plasma of subjects with IGE with absence seizures

### **2.3 Exploratory Objectives**

- To assess the exposure-response and exposure-safety relationships for plasma CX-8998 and its metabolites (including, but not limited to, M01 and M02); results to be reported separately from the clinical study report
- To evaluate the PD effects of CX-8998 as measured by EEG

## **3 STUDY DESIGN AND ENDPOINTS**

[figure not shown]
### **3.1 Study Type**

This is a Phase 2a, multicenter, open-label study consisting of a screening period of up to 4 weeks, a 4-week dose-titration treatment period to dose of up to 10 mg BID of CX-8998, and a 1-week safety follow-up period following the last dose of study medication.

### **3.2 Schematic of Study Design**

The study design schematic is shown in [Figure 6](#).

**Figure 6 Schematic of Study Design**

### **3.3 Endpoints**

#### **3.3.1 Primary Endpoint**

Safety and tolerability endpoints:

- Treatment-emergent adverse events (TEAE),
- Changes from baseline in QTcF and other ECG parameters,
- Changes from baseline in clinical safety laboratory assessments (clinical chemistry, hematology, and urinalysis),
- Changes from baseline in vital signs,
- Number (%) of subjects who did not complete the study due to TEAEs
- Number (%) of subjects with SAEs
- Number (%) of subjects with adverse events of special interest (AESI):
  - Increased seizure frequency
  - New seizure types
  - Status epilepticus
- Columbia-Suicide Severity Rating Scale (C-SSRS)
- University of Miami Parkinson's Disease Hallucinations Questionnaire (UM-PDHQ)

#### **3.3.2 Secondary Endpoints**

- Plasma PK parameters:  $C_{\max}$ ,  $T_{\max}$ ,  $C_{\min}$ , and partial  $AUC_{0-4h}$  for CX-8998 and metabolites (including, but not limited to, M01 and M02)
- Additional CX-8998 PK parameters ( $CL/F$ ,  $V_z/F$ ,  $t_{1/2}$ ) may be estimated, pending performance of a population PK analysis with data pooled from several studies (to be reported separately from the clinical study report).

#### **3.3.3 Exploratory Endpoints**

- Change in frequency (number of seizures per hour) of absence seizures as defined by a 3-Hz spike and wave lasting  $\geq 3$  seconds as determined by HV (HV period 1 + HV period 2)
- Change in frequency (number of seizures per hour) of absence seizures as defined by 3-Hz spike and wave lasting  $\geq 3$  seconds during wakefulness as determined by 6.5-hour video-EEG
- Time to absence seizure occurrence during HV (HV period 1 + HV period 2)
- Percent of subjects with a shift in occurrence of absence seizure during HV (e.g., shift for seizure occurring in HV period 1 or HV period 2 to no seizures occurring during either HV period; shift from absence seizure occurring to HV period 1 to HV period 2)
- Change from baseline to end of treatment in absence seizure-free days based on seizure diary
- Absence of photic response in subjects who had photic response during the baseline video-EEG

- Change in the Seizure-related Disability Assessment Scale (SERDAS)
- Relationship between the EEG parameters and the PK of CX-8998
- Exposure-response and exposure-safety relationships using plasma concentrations of CX-8998 and its 2 primary metabolites (M01 and M02) in population PK/PD analyses (to be reported separately from the clinical study report)

## **4 STUDY DRUG**

### **4.1 Supply and Storage**

CX-8998 will be supplied as 2 mg capsules. All manufacturing and packaging activities will be performed according to current Good Manufacturing Practices (cGMP) guidelines.

Study drug supplies will be stored securely in a temperature-controlled storage area (a locked cupboard or pharmacy with limited access). Only authorized personnel will have access to the study drug. The study site personnel at each site will be responsible for correct storage and handling of the study drug.

Supplies of study drug should be stored at 20°C to 25°C. Temperature excursions are permitted between 15°C to 30°C.

### **4.2 Packaging and Labeling**

Study medication will be supplied in 60-cc white HDPE bottles with 33-mm polypropylene, white, child-resistant closures. Bottles will contain 62 capsules per bottle. The bottles will be appropriately labeled. The affixed label will have spaces for entering the subject number and subject initials. At the time of dispensing, the subject number and subject initials will be entered onto the appropriate lines on the label.

The product label will contain the following information in the English language:

- Protocol number: CX-8998-CLN2-002
- Kit number (and bottle number)
- Storage conditions
- The sentence, "Caution: New Drug – Limited by Federal (or United States) law to investigational use"
- Name and address of the sponsor

## 4.3 Administration

CX-8998 will be administered as:

1. Days 1 – 2: 2 mg (1 capsule) BID (4 mg/d);
2. Days 3 – 8: 4 mg (2 capsules) BID (8 mg/d);
3. Days 9 - 14: 6 mg (3 capsules) BID (12 mg/d);
4. Days 15 – 20: 8 mg (4 capsules) BID (16 mg/d);
5. Days 21 - 26: 10 mg (5 capsules) BID (20 mg/d).

Study drug should be administered with food. Subjects should be instructed to take their daily dose at approximately the same times each day. Consecutive doses should be taken no closer than 10 hours and no later than 14 hours (every 12 hours  $\pm$  2 hours). Subjects will remain under observation for at least 4 hours post-dosing prior to discharge at Visit 1.

At the Day 26 clinic visit at which 2 postdose PK blood draws,  $>2$  hours apart, are scheduled to be obtained, subjects will take the morning dose at the appropriate time. Both the time of the morning dose and the time of the PK blood draw will be recorded.

A missed dose ( $>14$  hours since the prior dose) should be skipped and should not be “doubled-up” or “made up”; the next dose should be taken 24 hours from the last administered dose. If the subject experiences emesis following the dose, that dose should not be re-taken; instead the next dose should be taken 24 hours from the last administered dose without emesis. If emesis occurs, the subject should contact the investigator or qualified designee at the study site for guidance on management of the emesis.

Treatment compliance will be assessed as described in [Section 4.5.1](#).

Subjects experiencing specified AEs will have their dose adjusted. See [Section 4.6](#) for details on dose adjustments.

## 4.4 Subject Stopping Rules

Study drug dosing for an individual subject will be permanently discontinued for intolerable AEs that do not resolve to mild in severity (as defined in [Section 10.2.2.2](#)) or baseline within 48 hours of suspension of dosing and for study drug-related SAEs.

Administration of the study treatment will be discontinued if any of the following liver chemistry stopping criteria is met:

- Serum alanine aminotransferase (ALT) or aspartate aminotransferase (AST)  $\geq 3 \times$  ULN (upper limit of normal) and total bilirubin level  $\geq 2 \times$  ULN  
NOTE: Serum bilirubin fractionation should be performed if testing is available. If fractionation is unavailable, urinary bilirubin is to be measured via dipstick (a measurement of direct bilirubin, which would suggest liver injury).
- Serum ALT or AST  $\geq 5 \times$  ULN
- Serum ALT or AST  $\geq 3 \times$  ULN if associated with the appearance or worsening of rash or hepatitis symptoms (fatigue, nausea, vomiting, right upper quadrant pain or tenderness, fever, rash, or eosinophilia)

Any laboratory value that exceeds these limits should be repeated as soon as possible and, if confirmed, study treatment should be immediately discontinued. If a repeat laboratory assessment cannot be obtained within 3 days after receipt of the result showing the abnormal value, study drug should be discontinued.

A subject who meets the following ECG criteria will have study treatment discontinued:

- QTcF >500 msec or uncorrected QT >600 msec
- an increase in QTcF by  $\geq 60$  msec from Day 1 predose (baseline) with an absolute value of QTcF  $\geq 450$  msec (males) or  $\geq 470$  msec (females)

Treatment must be discontinued immediately in any subject who experiences a GTCS during the study if the subject had not had a GTCS prior to study entry. Subjects with worsening of seizures during the study should have treatment discontinued per investigator discretion. Unless consent for further follow-up is withdrawn, subjects who discontinue study drug for safety reasons should be followed in accordance with the schedule detailed in [Table 3](#).

Other reasons for treatment termination are provided in [Section 6.4](#).

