## 4.6 Dose Adjustments / Toxicity Management

Adverse events will be graded for intensity by the investigator (see [Section 10.2.2.2](#)).

Dosing will be discontinued for all study drug-related SAEs.

A member of the study staff will contact any subject who is suspected of experiencing neuropsychiatric AEs to determine the need for an unscheduled visit before further dose escalation may proceed. Subjects who are experiencing any AEs may also be asked to return for an unscheduled visit. Subjects who are suspected of experiencing a neuropsychiatric event should be seen in person.

In all subjects with intolerable AEs (as defined in [Section 10.2.1](#)) that are considered related to study drug, treatment should be suspended for up to 48 hours or until the AE resolves to a tolerable level of severity, whichever is earlier. In subjects who are unable to tolerate 6 mg BID, 8 mg BID or 10 mg BID, dosing may then be resumed at a previously tolerated lower dose. Only a single dose-step reduction (i.e., 10 mg BID to 8 mg BID, 8 mg BID to 6 mg BID, or 6 mg BID to 4 mg BID) is permitted. Reescalation of the dose is NOT permitted. Dosing should be discontinued if there is recurrence of intolerable AEs after the dose reduction. Subjects who experience intolerable AEs while receiving the 2 mg BID or 4 mg BID dose will be discontinued from treatment. Table 2 details dose reductions by dose level.

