**Table 2 Study Drug Dose Reduction for Intolerable AEs**

Dose and Schedule of Study Drug	Dose Reduction
2 mg BID	Remove from treatment 
4 mg BID	Remove from treatment
6 mg BID	4 mg BID
8 mg BID	6 mg BID
10 mg BID	8 mg BID

1 – Subjects who are removed from treatment for AE(s) should be followed for resolution of the AE(s) and should complete all assessments scheduled for the End-of Study (EOS)/Follow-up (FU) Visit, as well as all assessments that they are capable of completing on the scheduled visit day if the decision to remove from treatment is made on a scheduled visit day. Likewise, if the investigator plans to temporarily interrupt dosing because of an AE and the decision is made on a scheduled visit day, then the subject should complete all scheduled assessments that they are capable of completing on the visit day on which they appear.

All subjects who discontinue treatment due to AEs will be followed for AE outcome. All AEs should be followed for resolution or for 30 days from the last dose of study drug, whichever is shorter.

The Study Safety Representative should be notified of all dose reductions as soon as is feasible.

All subjects who discontinue treatment due to AEs will be followed for AE outcome. All AEs should be followed for resolution or for 30 days from the last dose of study drug, whichever is shorter.

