## **6.4 Withdrawal of Subjects and/or Discontinuation of Treatment**

A subject should be withdrawn from the study for any of the following:

- 1) Withdrawal of subject consent.
- 2) Subject is lost to follow-up.
- 3) Investigator determines that withdrawal from the study is in the best interest of the subject.
- 4) Subject is noncompliant with protocol-mandated activities.
- 5) Occurrence of any intercurrent condition, injury, or disease that becomes apparent during the study and necessitates the termination of the subject from the study.
- 6) Administrative reason (e.g., termination of the clinical study by a regulatory agency or the sponsor).

A subject should be discontinued from treatment for any of the following (see also [Section 4.4](#)):

- 1) Occurrence of defined unacceptable toxicity ([Section 4.6](#)).
- 2) Investigator determines that discontinuation of treatment is in the best interest of the subject.
- 3) Occurrence of any intercurrent condition, injury, or disease that becomes apparent during the study and necessitates the discontinuation of treatment.
- 4) Pregnancy.
- 5) Subjects who answer "yes" to Suicidal Ideation item 4 or 5 on the C-SSRS during the study must be withdrawn from the study treatment. Investigators should also withdraw subjects from treatment if, in the judgment of the investigator, the subject develops other indicators of significant risk of suicide. In the event that suicidal ideation is observed in any study subject, the investigator will manage the situation as he/she deems medically and psychiatrically appropriate.

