#### Intolerable Adverse Event

An intolerable AE is one that is considered by the investigator to be related to study drug ([Section 10.2.2.3](#)) AND is either a severe or life-threatening event ([Section 10.2.2.2](#)) OR is a mild or moderate event that prompts the subject to express a desire to discontinue dosing. Dose adjustments for intolerable AEs are described in [Section 4.6](#).

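### Protocol 4.4 and 4.6 set different conditions for restarting drug after an intolerable related AE at 6, 8 or 10 mg BID, and no text says which governs

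*Protocol*

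**What the plan says.** **Protocol 4.4 (Subject Stopping Rules)** is mandatory. Dosing stops permanently for "intolerable AEs that do not resolve to mild in severity", as graded in 10.2.2.2, or to baseline, within 48 hours of suspending drug. It also stops for drug-related SAEs.

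**Protocol 4.6 (Dose Adjustments / Toxicity Management)** governs the same suspension: "treatment should be suspended for up to 48 hours or until the AE resolves to a tolerable level of severity, whichever is earlier". For subjects who could not tolerate 6, 8 or 10 mg BID, "dosing may then be resumed at a previously tolerated lower dose". The reduction is limited to one step, with no re-escalation. At the two lowest levels there is no such option: "Subjects who experience intolerable AEs while receiving the 2 mg BID or 4 mg BID dose will be discontinued from treatment". Section 4.6 does not mention mild or baseline, does not cite 4.4, and does not say what a tolerable level is.

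**Protocol 10.2.1** calls a drug-related AE intolerable if it is severe or life-threatening, or if it "is a mild or moderate event that prompts the subject to express a desire to discontinue dosing". Under 10.2.2.2, moderate is a separate grade above mild and includes AEs that limit instrumental daily activities such as shopping or managing money.

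**Protocol 10.4** repeats the choice between stopping and stepping down at 6, 8 or 10 mg BID without the mild-or-baseline condition. A separate bullet refers in general terms to 4.4 for the individual dose-modification and stopping rules.

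**The concern.** Both sections address the same moment: drug has been suspended for an intolerable related AE, and the investigator must decide whether it may be restarted. Section 4.4 decides by severity grade. Section 4.6 decides by tolerability, or by the end of 48 hours. Under 10.2.1 a moderate AE becomes intolerable through the subject's wish to stop, so it may come to be regarded as tolerable without any change of grade.

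Two things are at stake. A subject could be re-dosed while a related AE still limits daily activities, where 4.4 calls for a stop. And two sites, each following the text, could handle the same case differently. Protocol 10.2.2.4 codes a reduced dose and a discontinued drug as separate actions. The SAP summarises dose reductions (5.1) apart from TEAEs leading to discontinuation of study treatment (5.3.2.3). Safety and tolerability is the primary objective, so the classification matters.

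**Working it through.** There is no plan figure to reproduce and no sample-size or power formula is involved. The check sets the two rules side by side for each state the AE can be in.

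**Step 1: scope.** Drug-related SAEs drop out because 4.4 and 4.6 both stop dosing. Intolerable AEs at 2 or 4 mg BID drop out because 4.6 and Table 2 remove the subject. What remains is a related, non-serious, intolerable AE at 6, 8 or 10 mg BID.

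**Step 2: compare the rules 48 hours after suspension.**

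| State of the AE | 4.4 | 4.6 | Agree? |
|---|---|---|---|
| Baseline | no stop required | restart allowed | yes |
| Mild, subject willing | no stop required | restart allowed | yes |
| Mild, subject still wants to stop | no stop required | restart allowed at 48 hours | yes |
| Moderate, subject willing | permanent stop | restart allowed if willingness makes it tolerable, or at 48 hours | no |
| Moderate, subject still wants to stop | permanent stop | restart allowed only by the 48-hour limit | no |
| Severe | permanent stop | restart allowed only by the 48-hour limit | no |

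Agree: 3. Differ: 6 − 3 = 3. Of those 3, the last two arise only if the end of the 48-hour suspension is itself read as permission to restart, which leaves 3 − 2 = 1 practical conflict: moderate and willing. These are counts of states, not probabilities.

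**Step 3: look for text that settles precedence.**
- 4.3 and 10.2.1 send the reader to 4.6 for dose adjustments.
- 6.4 lists grounds for stopping treatment, refers to 4.4 in its lead-in, and cites 4.6 for unacceptable toxicity.
- 10.4 refers to 4.4 generally, but states the step-down option without the condition.
- Table 2 gives dose levels only.
- The SAP is silent on the point.

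None of these says which section prevails.

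**Step 4: scale of one reclassification (illustration only).** With the planned maximum of about 15 subjects, one subject coded as discontinued instead of reduced moves each of those percentages by 1/15 = 6.7 points.

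**The case against.** The strongest reply is that the sections fit together. Section 4.6 caps the suspension at 48 hours, and 4.4 says what follows if the AE has not improved enough by then. A permissive *may* in 4.6 does not override a mandatory *will* in 4.4, and both 6.4 and 10.4 point to 4.4. This is a reasonable reading and probably the intended one. It rests on inference, however, because 4.6 sets its own end to the suspension and never mentions 4.4.

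A second reply concerns 10.2.1. If an AE stops being intolerable once the subject is willing to go on, 4.4 is arguably no longer triggered. If the label stays once the wish has been expressed, a still-moderate AE has not clearly become tolerable. This has force: the conflict depends on how an undefined term is read. But 4.4 tests the AE that led to suspension against mild or baseline, not against willingness, so the two sections still ask different questions.

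A third reply is that safeguards exist. "Dosing should be discontinued if there is recurrence of intolerable AEs after the dose reduction". "The Study Safety Representative should be notified of all dose reductions as soon as is feasible". Re-escalation is barred, and under 6.4 treatment stops when the "Investigator determines that discontinuation of treatment is in the best interest of the subject". Early discontinuations are also reported to the Study Safety Representative (6.4.1), so one role would see both outcomes. These safeguards limit the harm, but they act after re-dosing or at discretion, and none supplies the missing condition.

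**Conclusion.** The point holds as a limited inconsistency between two individual-subject safety rules. It affects related, non-serious intolerable AEs at 6, 8 or 10 mg BID. Its practical core is one state: still moderate at 48 hours in a subject now willing to continue. It assumes that an investigator may treat that AE as tolerable, which the text neither says nor rules out.

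Three stronger readings are not supported:
- A reader might infer that the protocol plainly authorises re-dosing a severe AE after 48 hours. A related severe AE is always intolerable under 10.2.1, so this rests only on taking the 48-hour limit literally and ignoring the mandatory stop in 4.4.
- A reader might infer that restarting before 48 hours breaches 4.4. It does not, because 4.4 allows up to 48 hours for resolution.
- A reader might infer that trial results were affected. SAP 1.1 states that nobody enrolled under amendments 4 and 5, and this protocol text carries the changes it attributes to them (video-EEG, no Day 27 dose). Whether amendment 3 used the same dose-adjustment wording cannot be seen. The documents give no basis for a frequency.

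**What to change.** In 4.6, replace the tolerable-level criterion with *resolves to mild in severity (Section 10.2.2.2) or baseline*. State that dosing may resume one step lower only if this is reached within 48 hours of suspension, and that otherwise study drug is permanently discontinued per Section 4.4. In 10.4, add *subject to Section 4.4* to the dose-decrease sentence. Leave 4.4, 10.2.1, Table 2, the single-step limit and the rule at 2 and 4 mg BID unchanged.

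Do not add a new mandatory stop for a mild AE in a subject who still wishes to stop. Section 4.4 does not require one. Restarting remains optional in that case.

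The cost is a short text change made through a protocol amendment. Because it bears on subject safety, 12.1.1 would class it as substantial, with submission to the regulatory authorities and the IRB. Visits, data collection and sample size do not change. Subjects still moderate at 48 hours would stop instead of stepping down, as 4.4 already requires.
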